2.1 Objectives and Hypotheses

2.1.1 The primary objectives of this proposed study in persons with fibromyalgia and comorbid insomnia are:

1) to assess the effect of suvorexant 20 mg versus placebo on polysomnographic (PSG) measures of sleep.

2) to assess the effect of suvorexant 20 mg versus placebo on next day measures of sleepiness/fatigue.

3) to assess the effect of suvorexant 20 mg versus placebo on next day measures of nociception and pain.

2.1.2 The clinical hypotheses to be tested are:

1) relative to placebo suvorexant 20 mg will increase PSG sleep efficiency and reduce sleep latency and wake after sleep onset in persons with fibromyalgia and comorbid insomnia.

2) relative to placebo suvorexant 20 mg will reduce self-reported next-day pain and nociceptive sensitivity as measured by Finger Withdrawal Testing (FWT) in persons with fibromyalgia and comorbid insomnia.

3) relative to placebo suvorexant 20 mg will reduce self-reported next-day fatigue and normalize Multiple Sleep Latency Test (MSLT) scores in persons with fibromyalgia and comorbid insomnia.

2.2 Background and Rationale

Typically insomnia is co-morbid with various medical and psychiatric disorders and among the disorders frequently co-morbid with insomnia are the various chronic pain disorders. A prevalent musculoskeletal chronic pain disorder is fibromyalgia in which pain is widespread and not specifically localized (1). Its etiology is unknown, although a prominent hypothesis suggests the pain is associated with enhanced central nervous system sensitization shown over all sense modalities (2). Between 60-80% of fibromyalgia patients complain of sleep disturbance, which most typically is a sleep maintenance problem, a complaint which has been confirmed with polysomnography (PSG). Another important persisting symptom in fibromyalgia is daytime sleepiness and fatigue, which may relate to the disturbed sleep of fibromyalgia or the underlying pathophysiology of the disorder, putative pro-inflammatory cytokine activation.

The PSG studies in fibromyalgia, dating to as early as 1975, have consistently reported reduced total sleep time relative to age-matched controls, primarily due to increased wake time after sleep onset (WASO) (3). However, despite having reduced nocturnal sleep compared to

age-matched healthy controls and reporting elevated levels of daytime sleepiness and fatigue like patients with rheumatoid arthritis, patients with fibromyalgia show elevated daytime arousal on an objective measure of daytime sleepiness/alertness, the Multiple Sleep Latency Test (MSLT) (4). Elevated MSLT latencies, despite shorter total sleep times, have also been seen in people with primary insomnia, which is consistent with the sensory hypersensitization model of fibromyalgia (2).

It has now become clear that the relation of sleep and pain is bidirectional; acute and chronic pain are associated with disturbed sleep and shortened and disturbed sleep enhances pain. Experimental studies have shown that reduced and fragmented sleep in pain-free normals increases their pain sensitivity and daily self-report studies in chronic pain patients have shown a poor night of sleep is followed by enhanced next-day pain (3). In mediation analyses of large clinical data sets it is found that the sleep-pain side of the bidirectional relation, as opposed to the pain-sleep side, accounts for the greater variance (5). These data then would suggest that improving sleep in chronic pain disorders should attenuate daytime pain.

Drugs from a number of different drug classes have been assessed as treatments in chronic pain disorders including analgesics, antidepressants, antiepileptics, and hypnotics. In many of these studies pain is the major study focus and if sleep is measured, it is a secondary outcome and typically only measured by self-report. Further, rarely are patients in these studies specifically included for the presence of co-morbid insomnia and degree of sleep disturbance.

While analgesics, antidepressants, and antiepileptics are typically used and studied in chronic pain disorders, only a few studies have assessed hypnotics and with quite mixed results. In fibromyalgia patients zolpidem (6), but not zopiclone (7), improved some of the sleep measures, but neither drug improved pain. Triazolam improved sleep and pain in patients with rheumatoid arthritis (8), whereas zopiclone only improved pain (9). A large (N=153) study of eszopiclone, the S isomer of zopiclone, assessed its sleep and pain effects in patients with insomnia co-morbid with rheumatoid arthritis (10). Eszopiclone compared to placebo improved self-reported measures of sleep and most all of the pain measures. Hospitalized patients with mucositis associated with chemotherapy for hematologic malignancies were randomized to 2 nights of eszopiclone or placebo (11). Pain scores throughout the day were improved with eszopiclone and patients reported increased sleep time and fewer awakenings.

Most of the drugs used to treat chronic pain facilitate inhibitory CNS mechanisms as their primary mechanism of action. Suvorexant, recently approved by the FDA for the treatment of insomnia characterized by difficulties with sleep onset and sleep maintenance, has a unique mechanism of action. Suvorexant is a selective antagonist for orexin receptors (OX1R and OX2R) (12). Orexins are considered to be involved in arousal and maintenance of the waking state. In support of this view, findings have shown that orexin neurons send dense projections to brain arousal areas including the locus coeruleus, tuberomammillary nucleus, and the basal forebrain cholinergic system (13). In PSG studies in healthy men, suvorexant 10 mg increased sleep efficiency and reduced WASO (14) and in patients with primary insomnia it increased sleep efficiency by reducing latency to persistent sleep (10 min of continuous sleep) and WASO (15).

As such, suvorexant may provide unique clinical benefit as a treatment in chronic pain conditions with co-morbid insomnia, and specifically for fibromyalgia with its putative central hyperarousal and hypersensization. Thus, this project proposes to study objective and clinical measures of sleep, pain, and daytime sleepiness and fatigue in patients with fibromyalgia and co-morbid insomnia while treated short-term with suvorexant 20 mg versus placebo.

2.3 Study Design

The study will be conducted as a double blind, placebo controlled, trial using a repeated measures design. Patients with fibromyalgia and co-morbid insomnia (n=30) will be treated for 9 nights each with suvorexant 20 mg and placebo with the order of treatments counterbalanced. The study will be registered on clinicaltrials.gov

2.4 Study Flowchart

Patients with fibromyalgia and co morbid insomnia will be recruited from the HFHS hospitals and clinics and from patient support groups in Metro Detroit. In our most recent study of fibromyalgia we were able to recruit 20 patients over a period of twelve months. Patients will be assessed clinically for fibromyalgia and insomnia using American College of Rheumatology (ARC) (16) and Diagnostic and Statistical Manual of Mental Disorders (DSM-5) (17) criteria, respectively. They will be screened by PSG for other primary sleep disorders and a sleep efficiency (sleep time/bedtime) of < 85%.

2.4.1 Inclusion Criteria

- Women with good psychiatric and stable physical health.
- Aged between 21 and 65 yrs old.
- Having a customary bedtime of 12 midnight or earlier, having at least 6 to 8 hrs in bed on average.
- Meeting the American College of Rheumatology criteria for fibromyalgia.
- Having wide spread pain, which includes pain in all four quadrants; including symptoms and/or complaints of fatigue, waking non-refreshed and cognitive symptoms.
- Current average pain severity score \geq 4 on the Brief Pain Inventory at screening.
- Meeting the Diagnostic and Statistical Manual of Mental Disorders, fifth edition, criteria for insomnia and additionally with a sleep efficiency of < 85% on a screening PSG.

2.4.2 Exclusion Criteria

- Pain symptoms (unrelated to fibromyalgia) that could interfere with the interpretation of outcome measures; regional pain syndromes (eg. back, neck); multiple surgeries; pain from a traumatic injury; a confirmed current or previous diagnosis of rheumatoid arthritis, or similar disorders, inflammatory arthritis, or other autoimmune disease, osteoarthritis, tendonitis, unstable medical or psychiatric disorders.
- Any condition that could confound assessment of sleep, including depression (scoring 14 > on the Hamilton Depression Rating Scale (HAM-D), anxiety (scoring 24> on the Hamilton Anxiety Rating Scale (HAM-A), other psychiatric disorders, chronic medical conditions (e.g. liver disease, heart failure) or uncontrolled medical conditions.
- Consuming >14 alcoholic beverages per week (and/or >5 or > 4 drinks per single occasion for males and females, respectively) and >300mg of caffeine per day.
- The inability to discontinue, hypnotics or antidepressants.
- Substance abuse within the last 2 years and/or a failed urine drug screen;
- Primary sleep disorders, including narcolepsy, or circadian rhythm sleep disorder, excluding insomnia;
- Respiratory disturbances [apnea hypopnea index] or periodic limb movement arousal index greater than 10 per hour of sleep.
- Having a history of frostbite and/or Raynaud's syndrome.
- Current pregnancy or breast-feeding.

While patients will be told to discontinue hypnotic use, they will be allowed use of pain medications throughout the study to be recorded in a daily diary, as long as they are using a stable dose on a regular basis. The one exception will be that sedating tricyclic antidepressant use will be excluded. Patients will be asked to discontinue their antidepressant or hypnotic use two weeks before entering the study protocol.

Those qualifying will receive suvorexant 20 mg and placebo for each of 9 nights in a cross over design with 7 nights of washout between treatments. PSGs will be collected on nights 7 and 8 of each crossover treatment arm. During day 8 of each treatment a MSLT (1000, 1200, 1400, and 1600 hr) will be done, and on days 1 and 8 nociceptive sensitivity [finger withdrawal latency (FWL)] testing to a radiant heat stimulus (1100 and 1500 hr) will be conducted. On days 1 and 8 self-reported mood and pain indices will also be completed prior to each nociceptive sensitivity test.

2.5 Study Procedures

2.5.1 Polysomnography (PSG)

For each PSG night, participants will arrive 2 hours prior to their reported bedtime to complete check-in procedures and undergo electrode placement for standard 8-hr PSGs (18). Bedtimes will be determined using the participant's self-reported normal sleep schedule with

time in bed fixed to 8 hrs. For the screening PSG, central and occipital electro-encephalogram (EEG) leads (C3-A2 and O2-A1) will be placed to measure EEG activity and left and right horizontal electroculograms (EOG) will be used to measure eye movements. A V5 electrocardiogram (ECG) lead and a sub-mental electromyogram (EMG) lead will be placed. Airflow (by pressure transducer), body position via video recording, thoracic and abdominal excursion (inductance plethysmography), oxygen saturation (finger pulse oximetry), leg movement (with electrode over left anterior tibialis muscle), and sound will also be recorded. For the study nights 8 and 9 the 8-hr PSGs will consist of continuous monitoring of two channels of EEG (C3-A2 and O2-A1), left and right EOGs, submental EMG and V5 ECG.

All recordings will be scored in 30 second epochs for standard sleep stages according to the standards of Rechtschaffen & Kales (18). Scoring will be done by technicians with established intra-laboratory scoring concordance and verified by review of the PI or Col. Respiratory events and periodic leg movement events will be scored according to established AASM published criteria (19). Based on the screening PSG, patients with respiratory or periodic leg movement event indices of > 10 will be excluded.

2.5.2 Daytime Sleepiness/Alertness (MSLT)

Each test of the MSLT will be conducted according to the standard research MSLT protocol (20). Participants will be placed in bed in quiet, darkened rooms and instructed to close their eyes, relax, and fall asleep. Each test is concluded after 20 minutes of continuous wake or after three continuous 30s epochs of stage one sleep, or one epoch of any other sleep stage. Latency to sleep onset will be scored as min to the first epoch of sleep or 20 min if sleep did not occur. The latencies for the 4 tests are averaged to generate a single latency value.

2.5.3 Nociceptive Sensitivity (FWL)

A radiant heat method will be used to assess nociceptive sensitivity (21). Participants are seated in a comfortable chair at a desk with their hand resting on top of a metal box housing the heat source. The pad of the index finger (fingerprint whorl) is centered over a 3-mm hole

through which the heat radiates. The heat source is a 100-watt projection bulb, located 10 mm from the finger. A potentiometer controls the amount of current delivered to the light bulb, thereby varying heat intensity. On each trial, participants are instructed to place their index finger on the hole through which the heat source radiates and to withdraw their index finger when they first began to feel pain. Once finger withdrawal occurs, a photocell (mounted on a post located above the finger) detects the light (from the bulb underneath) and stops a digital timer connected to the circuit. Both index fingers are tested and the heat intensities are adjusted on each trial such that five different heat intensities (ranging from 83.4 to 101.6 degrees Fahrenheit, measured at steady-state after 10-sec duration) are presented in a randomized order. The FWL from left and right index fingers are averaged. The primary dependent measure is mean FWL (to a resolution of 0.01 sec) for each of the 5 heat intensities.

Patients initially will undergo a training session to familiarize themselves with the nociceptive testing equipment and procedures. The threshold at which a finger withdrawal response is elicited for each participant is established. The threshold radiant heat intensity is defined as the intensity that produces FWL of <21 sec.

As to the validity of the radiant heat method, our studies have shown FWL is systematically related to stimulus intensity (greater intensity = shorter FWL), basal level of sleepiness/alertness (greater sleepiness = shorter FWL), and codeine versus placebo (codeine = longer FWL) (21). Importantly, in healthy normals without sleep disturbance reducing sleep time by as little as 2 hrs reduces FWL and increasing sleep time by as little as 1 hr increases FWL (22,23). Further, in patients with moderate to severe obstructive sleep apnea (OSA) treated with Continuous Positive Airway Pressure (CPAP), thereby eliminating the OSA and consolidating sleep, FWL is increased and when the CPAP is discontinued for two nights FWL is again reduced (24).

2.5.4 Morning Self-reported Sleep and Previous Day Pain Assessment

Each morning after arising participants will complete a brief questionnaire regarding the previous night's sleep and the previous day's pain. The Red Cap questionnaires will be

accessed over the internet by participants' using their own password protected login identification credential with a daily time-limited completion interval (before 12 noon each day). The questionnaire will query regarding latency to fall asleep, wake time after falling asleep, total sleep time, pain disruption of sleep and alertness after awakening in the morning. Daytime pain the previous day will be assessed using the Short-Form McGill Pain Questionnaire (28).

2.5.5 Safety Monitoring

Each participant will complete the Columbia Suicidality Scale at screening and on study day 1 and 8. Additionally the Hamilton Depression Rating Scale (HAM-D) and Hamilton Anxiety Rating Scale (HAM-A) will also be completed on those days. The rating scales will be administered between the first and second nociceptive sensitivity testing (at approximately 1130 hr) on each day. Changes on any of these scales from the scores established at the baseline will be reported as AEs (see below). On day three of each of the treatment periods the patient/subjects will be contacted by phone to determine whether they are experiencing AEs.

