2.9 Adverse Event Reporting

Adverse events (AE) will be collected and reported to the study sponsor and the HFHS IRB as blinded events quarterly. Serious adverse events (SAEs) will be reported as unblinded events to the study sponsor, the HFHS IRB and the FDA. SAEs will be reported within 48 hrs of becoming aware of the event. Initial reports will be followed by reports of the resolution of the SAE.

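### Section 2.5.5 makes any change on the suicidality, depression or anxiety scale an adverse event, so improvements are counted as AEs along with worsening

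*Combined protocol and SAP*

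**What the plan says.** Section 2.5.5 (Safety Monitoring) sets the schedule: "Each participant will complete the Columbia Suicidality Scale at screening and on study day 1 and 8". It adds that the "Hamilton Depression Rating Scale (HAM-D) and Hamilton Anxiety Rating Scale (HAM-A) will also be completed on those days". The reporting rule follows: "Changes on any of these scales from the scores established at the baseline will be reported as AEs". The rule is worded as an instruction. It states no direction, no minimum size and no step of clinical judgement. It does not say which visit supplies the baseline.

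The rule ends with a pointer to later text. That text is section 2.9 (Adverse Event Reporting), which opens: "Adverse events (AE) will be collected and reported to the study sponsor and the HFHS IRB as blinded events quarterly". The rest of 2.9 deals with serious events: they go unblinded to the sponsor, the IRB and the FDA within 48 hours, with follow-up to resolution. It does not define an adverse event.

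Section 2.7.1 (Statistics) plans analyses of sleep, sleepiness/fatigue and pain. It plans none of adverse events or of the three scales.

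**The concern.** An AE count is read as a measure of harm. A rule without direction adds events that are not harm: a HAM-D or HAM-A score that falls because the patient feels better, and a score that falls by chance between two ratings. The counts sent to the sponsor and the IRB each quarter would then mix worsening and improvement. So would any AE table by treatment drawn up after unblinding.

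The wording also creates a problem of consistency. Staff who follow it literally report every change, and staff who assume that worsening was meant report only part of them. The second reading is probably what was intended, but it departs from the written rule. Two raters could thus produce different AE counts from the same scores.

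**Working it through.** The plan gives no AE rate and no variability for these scales, so it has no figure to reproduce. The check is first of the text, then an illustration on stated assumptions.

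**Does any other section narrow the rule?**
- Section 2.5.5: no direction and no size.
- Section 2.9: reporting route, blinding and timing only.
- Section 2.7.1: no analysis of AEs or of these scales.
- Section 2.4.2 (Exclusion Criteria): the exclusion begins "Any condition that could confound assessment of sleep, including depression (scoring 14" and applies at HAM-D of 14 or more and HAM-A of 24 or more. Non-zero scores below those limits are allowed at entry, so scores can fall as well as rise.

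Nothing limits the rule to worsening.

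**How many comparisons does the rule apply to?** This depends on the unnamed baseline and on whether 'study day 1 and 8' means both periods. For HAM-D and HAM-A together, with n = 30 (section 2.3):

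| Reading | Comparisons per patient | In 30 patients |
|---|---|---|
| Screening is baseline; days 1 and 8 of both periods | 2 scales × 4 = 8 | 240 |
| Day 1 of period 1 is baseline | 2 × 3 = 6 | 180 |
| Day 1 of each period is its own baseline | 2 × 2 = 4 | 120 |
| A single pair of day 1 and day 8 | 2 × 1 = 2 | 60 |

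The number of opportunities for a scale-based AE varies fourfold with the reading.

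**What share would be improvements?** Treat the change in one scale at one visit as a normal variable with mean μ and SD σ, rounded to whole points. Then P(worse) = 1 − Φ((0.5 − μ)/σ) and P(improved) = Φ((−0.5 − μ)/σ). Both μ and σ are assumptions; σ is taken from 1 to 4 points.

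For μ = 0 and σ = 1, P(worse) = 1 − Φ(0.5) = 0.309 and P(improved) = Φ(−0.5) = 0.309. The other rows follow in the same way.

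| μ | σ | Worse | Improved | Any change | Of 30: any change | Of 30: worse |
|---|---|---|---|---|---|---|
| 0 | 1 | 0.309 | 0.309 | 0.617 | 18.5 | 9.3 |
| 0 | 2 | 0.401 | 0.401 | 0.803 | 24.1 | 12.0 |
| 0 | 3 | 0.434 | 0.434 | 0.868 | 26.0 | 13.0 |
| 0 | 4 | 0.450 | 0.450 | 0.901 | 27.0 | 13.5 |
| −2 | 1 | 0.006 | 0.933 | 0.939 | 28.2 | 0.2 |
| −2 | 2 | 0.106 | 0.773 | 0.879 | 26.4 | 3.2 |
| −2 | 3 | 0.202 | 0.691 | 0.894 | 26.8 | 6.1 |
| −2 | 4 | 0.266 | 0.646 | 0.912 | 27.4 | 8.0 |

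With no true change, half of the events are improvements whatever σ is. This follows from symmetry alone. With an assumed true improvement of 2 points, the share of improvements is 0.646/0.912 = 71% at σ = 4 and 0.933/0.939 = 99% at σ = 1. In that case the any-change rate (88 to 94%) is above its value under no change at the same σ, while the rate of worsening falls. The count then moves against the harm it is meant to show.

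**The case against.** The sentence stands under a safety heading and concerns adverse events, so the ordinary reader will take it to mean worsening. That is a fair guess at the intent, but the text does not say it and no other section supplies it.

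Several stronger inferences that a reader might draw are not supported:

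- *That a comparison of AEs between treatments is biased.* Section 2.7.1 plans no such comparison. Only the reported counts and any later descriptive table are affected.
- *That improvements are charged to suvorexant.* Routine AE reports are blinded, so they charge nothing to either treatment. The hypotheses in section 2.1.2 say that the drug "will reduce self-reported next-day fatigue and normalize Multiple Sleep Latency Test (MSLT) scores", and they also cover sleep and pain. They do not predict better mood or anxiety scores, so the 2-point improvement above is only a what-if.
- *That a suicidality signal would be lost.* A rule that reports every change reports every worsening. The suicidality scale is a separate instrument, and serious events go by their own 48-hour route.
- *That nearly every patient would have a scale-based AE.* One can assume that each score differs from baseline with probability 0.2, 0.3 or 0.5, independently, and take 8 comparisons. Then 1 − (1 − p)^8 gives 83%, 94% and 99.6%. With 2 comparisons the same formula gives 36%, 51% and 75%. The p values are not in the documents. Repeated scores set against one shared baseline are also not independent, and positive dependence lowers these percentages.

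These objections limit the consequence. They do not remove the defect in the rule.

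**Conclusion.** The point holds as a wrong reporting rule: followed exactly, it records improvements and chance decreases on three scales as adverse events. It inflates the AE counts in the quarterly reports and in any later table by treatment. No planned test, efficacy estimate or power figure changes.

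The amount of inflation cannot be derived from the documents. The one statement on size is conditional: if changes are symmetric about zero, about half of the scale-based AEs are improvements. Symmetry is itself an assumption. Patients who enter at or near zero have little room to fall, which would lower the share, and a general improvement during the study would raise it.

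**What to change.** In section 2.5.5:

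1. Replace the word 'Changes' with 'Worsening' in the reporting rule.
2. Name the visit that supplies the baseline score, and say whether one baseline serves both periods or each period has its own. State also whether the scales are given on days 1 and 8 of both periods. Section 2.4.2 has antidepressants and hypnotics stopped two weeks before entry, so the choice of visit may affect the scores.

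In section 2.7.1, add a descriptive table of all three scales by treatment and visit, so that changes in both directions remain visible.

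Whether a minimum size of worsening should apply is for the investigator and sponsor to decide. It is not part of this fix, because a threshold would take some worsenings out of AE reporting.

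The cost is a small change of wording and one extra summary table. Improvements would no longer appear in the AE listing, but the score table would still show them.
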